Appendix E. Revised International Working Group Response Criteria #

Category	Definition
Complete remission (CR) ¹	Bone marrow blasts < 5%; absence of blasts with Auer rods; absence of extramedullary disease; absolute neutrophil count > 1.0 x 10 ⁹ /L; platelet count > 100 x 10 ⁹ /L; independence of red cell transfusions
CR with incomplete recovery (CRi) ²	All CR criteria except for residual neutropenia (< 1.0 x 10 ⁹ /L) or thrombocytopenia (< 100 x 10 ⁹ /L)
Morphologic leukemia-free state ³	Bone marrow blasts < 5%; absence of blasts with Auer rods; absence of extramedullary disease; no hematologic recovery required
Partial remission	Relevant in the setting of phase 1 and 2 clinical trials only; all hematologic criteria of CR; decrease of bone marrow blast percentage to 5% to 25%; and decrease of pretreatment bone marrow blast percentage by at least 50%
Cytogenetic CR ⁴	Reversion to a normal karyotype at the time of morphologic CR (or CRi) in cases with an abnormal karyotype at the time of diagnosis; based on the evaluation of 20 metaphase cells from bone marrow
Molecular CR ⁵	No standard definition; depends on molecular target

Treatment Failure Criteria

Category	Definition
Resistant disease (RD)	Failure to achieve CR or CRi (general practice; phase 2/III trials), or failure to achieve CR, CRi, or PR (phase 1 trials); only includes patients surviving > 7 days following completion of initial treatment, with evidence of persistent leukemia by blood and/or bone marrow examination
Death in aplasia	Deaths occurring > 7 days following completion of initial treatment while cytopenic; with an aplastic or hypoplastic bone marrow obtained within 7 days of death, without evidence of persistent leukemia
Death from indeterminate cause	Deaths occurring before completion of therapy, or < 7 days following its completion; or deaths occurring > 7 days following completion of initial therapy with no blasts in the blood, but no bone marrow examination available Patients who do not complete the first course of therapy
Relapse ⁶	Bone marrow blasts > 5%; or reappearance of blasts in the blood; or development of extramedullary disease
Molecular or cytogenetic relapse	Reappearance of molecular or cytogenetic abnormality

¹ All criteria need to be fulfilled; marrow evaluation should be based on a count of 200 nucleated cells in an aspirate with spicules; if ambiguous, consider repeat examination after 5 to 7 days; flow cytometric evaluation may help to distinguish between persistent leukemia and regenerating normal marrow; a marrow biopsy should be performed in cases of dry tap, or if no spicules are obtained; no minimum duration of response required.

² The criterion of CRi is of value in protocols using intensified induction or double induction strategies, in which hematologic recovery is not awaited, but intensive therapy will be continued. In such protocols, CR may even not be achieved in the course of the entire treatment plan. In these instances, the overall remission rate should include CR and CRi patients. Some patients may not achieve complete hematologic recovery upon longer observation times.

³ This category may be useful in the clinical development of novel agents within phase 1 clinical trials, in which a transient morphologic leukemia-free state may be achieved at the time of early response assessment.

⁴ Four studies showed that failure to convert to a normal karyotype at the time of CR predicts inferior outcome.

⁵ As an example, in CBF AML low-level PCR-positivity can be detected in patients even in long-term remission. Normalizing to 104 copies of ABL1 in accordance with standardized criteria, transcript levels below 12 to 10 copies appear to be predictive for long-term remission.

⁶ In cases with low blast percentages (5-10%), a repeat marrow should be performed to confirm relapse. Appearance of new dysplastic changes should be closely monitored for emerging relapse. In a patient who has been recently treated, dysplasia or a transient increase in blasts may reflect a chemotherapy effect and recovery of hematopoiesis. Cytogenetics should be tested to distinguish true relapse from therapy-related MDS/AML.

CRh (complete response/remission with partial hematologic recovery) will also be reported as an outcome measure. CRh is defined as ≤ 5% blasts in bone marrow, no evidence of circulating blasts or extramedullary disease and partial recovery of peripheral blood counts (platelets > 50,000/μL, hemoglobin ≥ 7g/dL and absolute neutrophil count > 500/μL).

Progressive Disease*

Progressive disease for patients with AML is defined as:

- Greater than 50% increase in bone marrow blasts from the best assessment and at least 20% marrow blasts.
- Greater than 50% increase in the peripheral blood absolute blast count and at least an absolute blast count of 1000/cmm.
- Development of extramedullary disease. If the patient has extramedullary disease at baseline, then the development of a new site of disease.
- In patients who present with a bone marrow blast percentage sufficiently high to preclude the ability to determine disease progression by a > 50% increase in the marrow blast percentage, then disease progression will be determined by peripheral blood criteria or the development of new sites of extramedullary disease.

* Patients may remain on study treatment if the investigator believes the patient is deriving some benefit.

Relapse Criteria

Relapse after complete remission (**CR**) for patients with AML is defined as:

- recurrence of blasts in the marrow of $\geq 5\%$ (excluding increased blasts in the context of regenerating marrow)
- recurrence of leukemic blasts in the peripheral blood
- recurrence of leukemia at an extramedullary site
- recurrence of pre-treatment characteristic signs of morphological dysplasia
- recurrence of Auer rods

These response criteria were published in the 2010 paper, "Diagnosis and management of acute myeloid leukemia in adults: recommendations from an international expert panel, on behalf of the European LeukemiaNet" (Dohner et al, 2010), and are based on Revised IWG recommendations published in 2003 (Cheson et al, 2003).

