4.1 Inclusion Criteria

101. Subject has provided informed consent prior to initiation of any study-specific activities/procedures
102. Subjects ≥ 18 years of age at the time of signing consent
103. For R/R AML subjects only, AML as defined by the WHO Classification ([Appendix D](#)) as persisting or recurring following 1 or more treatment courses (exceptions noted in exclusion criteria). Subjects must have failed treatment with, be intolerant to, or must not be candidates for available therapies for the treatment of R/R AML (not applicable to MRD+ subjects)
104. For R/R AML subjects only, myeloblasts $\geq 5\%$ in bone marrow, as confirmed by immunophenotype by flow cytometry (not applicable to MRD+ subjects)
105. Eastern Cooperative Oncology Group (ECOG, [Appendix F](#)) Performance Status of ≤ 2
106. Renal function as follows:
 - serum creatinine < 2.0 mg/dL (176.84 $\mu\text{mol/L}$)
 - estimated glomerular filtration rate (eGFR) > 30 mL/min/1.73 m²
107. Hepatic function as follows:
 - aspartate aminotransferase (AST) and alanine aminotransferase (ALT) ≤ 3.0 x upper limit of normal (ULN)
 - bilirubin ≤ 1.5 x ULN (unless considered due to Gilbert's syndrome or hemolysis)
108. **(CLOSED)** Etanercept (Enbrel) substudy only:

No active tuberculosis in the setting of anti-TNF therapy

National guidelines should be followed for appropriate tuberculosis screening in the setting of anti-TNF therapy, including a minimum of:

 - Subject has a negative test for tuberculosis during screening defined as either:
 - Negative purified protein derivative (PPD) (< 5 mm induration at 48 to 72 hours after test is placed) OR
 - Negative Quantiferon test

Subjects with positive PPD and a history of bacillus Calmette-Guérin vaccination are allowed with a negative Quantiferon test.

Subjects with a positive PPD test (without a history of bacillus Calmette-Guérin vaccination) or subjects with a positive or indeterminate Quantiferon test are allowed if they have all of the following:

- no symptoms, per tuberculosis worksheet provided by Amgen
- documented history of a completed course of adequate treatment or prophylaxis (per local standard of care) prior to the start of investigational product
- no known exposure to a case of active tuberculosis after most recent prophylaxis
- no evidence of active tuberculosis on chest radiograph within 3 months prior to the first dose of investigational product

109. For the MRD+ Group, AML subjects in any CR/CRh/CRi:

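### At exactly 5% marrow blasts, the CRh definition overlaps R/R entry and Appendix E gives two relapse cut-offs, so response, DOR and (in the MRD+ group) RFS depend on which line is read

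*Protocol*

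**What the plan says.** **Entry.** Protocol Section 4.1, criterion 104, admits R/R subjects with 5% or more myeloblasts "in bone marrow, as confirmed by immunophenotype by flow cytometry". Criterion 109 admits MRD+ subjects who are in CR, CRh or CRi.

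**Response (Protocol Appendix E).** CR requires "Bone marrow blasts < 5%; absence of blasts with Auer rods; absence of extramedullary disease", plus recovered counts. CRi and MLFS keep the below-5% limit. Partial remission allows 5% to 25%, but only with at least a halving of the pretreatment percentage. CRh is added in a note below the table: at most 5% "blasts in bone marrow, no evidence of circulating blasts or extramedullary disease and partial recovery of peripheral blood counts", with platelets above 50,000/µL, hemoglobin at least 7 g/dL and neutrophils above 500/µL. No change from baseline is mentioned.

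**Relapse (Protocol Appendix E).** The treatment-failure table gives blasts above 5%, "or reappearance of blasts in the blood; or development of extramedullary disease". The later Relapse Criteria list, headed as relapse after CR, gives recurrence at 5% or more, "excluding increased blasts in the context of regenerating marrow". Footnote 6 asks for a repeat marrow at 5-10% to confirm relapse.

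**Use.** CRh counts as overall response in SAP Section 5 and in the R/R futility rule (Protocol Section 10.3, SAP Section 3.3). SAP Section 5 takes the DOR event from the revised IWG criteria, which is the title of Appendix E. It defines RFS, for the MRD+ group, by hematologic relapse or death. It gives no blast cut-off for either.

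**The concern.** Entry, response and relapse should not overlap. At 5% they do, in two separate ways.

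1. **Response.** CRh is the only response category that admits 5% blasts without a fall. An R/R subject who enters at 5%, with no circulating blasts or extramedullary disease and adequate counts, meets it before the first dose. Nothing in Sections 4.1 or 4.2 requires circulating blasts or low counts at entry. The R/R futility rule turns on one or two responders, so a single such subject can change the decision.
2. **Relapse.** A responder whose marrow returns to 5% has relapsed on one line of Appendix E and not on the other. That affects DOR event dates in the R/R expansion and RFS event dates in the MRD+ expansion. If it is left open, borderline cases will be settled after the data have been seen, in an open-label trial.

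**Working it through.** **Step 1. The lines side by side.** Each blast criterion is applied to three readings:

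| Marrow blasts | R/R entry (≥5%) | CR/CRi/MLFS (<5%) | CRh (≤5%) | Relapse, failure table (>5%) | Relapse, criteria list (≥5%) |
|---|---|---|---|---|---|
| 4.5% | no | yes | yes | no | no |
| 5.0% | yes | no | yes | no | yes |
| 5.5% | yes | no | no | yes | yes |

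Only the middle row conflicts. Partial remission does not apply to an unchanged 5%, because it needs a fall of at least half.

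**Step 2. Is exactly 5% an odd value?** Appendix E, footnote 1, specifies a 200-cell count, so 5% is 10 cells. The binomial probability of counting exactly 10 of 200 is 0.128 if true blasts are 5%, 0.101 at 4%, 0.106 at 6% and 0.041 at 3%. This is counting error only. It does not say how many enrolled subjects lie near 5%.

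**Step 3. Reproduce the plan's futility figures.** Inputs are the R/R rule (stop at 0/12, ≤2/18 or ≤3/24) and 40 subjects if not stopped. Responses are carried forward look by look with exact binomial probabilities, and paths that meet a stopping condition are removed.

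- True rate 0.10: the first look gives 0.90^12 = 0.282. Cumulative stopping is 0.282, 0.738 and 0.825, with average size 20.67. Protocol Table 28 states 0.28, 0.74, 0.82 and 20.7.
- True rate 0.15: 0.142, 0.486 and 0.575, average 27.03. Table 28 states 0.14, 0.49, 0.58 and 27.0.

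The remaining rows also agree to within 0.01 in probability and 0.1 in average size.

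**Step 4. Effect of one subject.** Two responders among 18 stops enrollment; three among 18 continues. At the end, 8/40 has an exact 80% interval of 12.0% to 30.4%, matching the plan's 12% to 30%. With one extra CRh, 9/40 gives 14.1% to 33.2%.

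**Step 5. Illustration of rate.** Let q be the share of true non-responders counted as CRh at an unchanged 5%. The documents give no value, so q is assumed. With true rate 0.10, the observed rate is 0.10 + 0.90q:

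| q | Observed rate | P(futility stop by 24 subjects) |
|---|---|---|
| 0 | 0.100 | 0.825 |
| 0.01 | 0.109 | 0.784 |
| 0.02 | 0.118 | 0.740 |
| 0.03 | 0.127 | 0.695 |
| 0.05 | 0.145 | 0.601 |

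**The case against.** **It is one value, with safeguards around it.** Footnote 6 asks for a repeat marrow at 5-10%, the Relapse Criteria list excludes regenerating marrow, and Protocol Table 25 (footnote a) requires flow-cytometric confirmation of blast assessments. Appendix E also classes failure to reach CR, CRi or PR in a phase 1 trial, with persistent leukemia, as resistant disease. These make a no-change responder less likely. They do not settle the matter: footnote 6 concerns relapse and not CRh, and it does not choose between the two symbols. The resistant-disease line leaves CRh out of its list of responses, so it adds a second label without removing the first.

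**The assumed rates may be high.** This stands. A true 5% marrow reads exactly 10/200 only 12.8% of the time. For a single assessment, q = 0.03 would need about 0.03/0.128 = 23% of non-responders to have a true 5% marrow, and q = 0.05 about 39%, all with CRh-level counts. Repeat assessments raise the chance, but the documents do not show such a case mix.

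**Tightening CRh removes only the exact 5% reading.** This also stands. A true 5% marrow reads below 10/200 about 45% of the time and can then meet the MLFS blast limit. The edit removes a definitional overlap; it does not remove counting error.

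**Readings that go too far.** A reader might infer that one unchanged R/R subject is eligible, a CRh responder and relapsed all at once. The documents do not support that: the ≥5% list needs a recurrence after CR, and the failure table needs more than 5%. A reader might also carry the problem to RFS in R/R subjects, but RFS is an MRD+ endpoint only.

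**Conclusion.** The point holds as a threshold conflict at a reading of exactly 5%. Followed literally, an R/R subject with an unchanged 5% marrow and CRh-level counts is a responder in the response rate and in the futility count. The relapse event for DOR has two contradictory cut-offs. RFS is exposed to the same two cut-offs through the MRD+ group, whose members may enter in CRh and so at 5%.

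The firm consequence is at the level of a single subject: 2/18 becomes 3/18 and a stop becomes a continue. The fall in stopping probability from 0.83 to between 0.78 and 0.60 rests wholly on an assumed miscounting rate of 1% to 5% among true non-responders at a true response rate of 10%. It shows sensitivity and is not an estimate. Table 28 itself is correct for the rule it describes.

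The documents also do not say whether the list headed as relapse after CR applies to subjects whose best response was CRh, CRi or MLFS.

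**What to change.** - In Appendix E, align the CRh blast limit with CR, CRi and MLFS (below 5%) for the response analysis, so that it no longer overlaps R/R entry.
- Reconcile the two relapse cut-offs in Appendix E to one value.
- State both in SAP Section 5, under overall response, DOR and RFS, and say whether the relapse rule applies to CRh, CRi and MLFS responders.

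**Cost.** The change is a few symbols in Appendix E and a short addition to the SAP. A borderline 5% subject would no longer count as a CRh responder. CRh is also an MRD+ entry state under criterion 109, so that eligibility text must be reconciled with the change. The R/R entry threshold and the futility boundaries need no change.

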Appendix F. Performance Status According to Eastern Cooperative Oncology Group (ECOG) Scale

ECOG Performance Status Scale	
Grade	Descriptions
0	Fully active, able to carry on all pre-disease performance without restriction.
1	Restricted in physically strenuous activity, but ambulatory and able to carry out work of a light or sedentary nature (eg light housework, office work).
2	Ambulatory and capable of all self-care, but unable to carry out any work activities. Up and about more than 50% of waking hours.
3	Capable of only limited self-care, confined to bed or chair more than 50% of waking hours.
4	Completely disabled. Cannot carry on any self-care. Totally confined to bed or chair.
5	Dead.

Source: Oken MM, Creech RH, Tormey DC et al.: Toxicity And Response Criteria Of The Eastern Cooperative Oncology Group. *Am J Clin Oncol* 1982; 5: 649-655

Appendix G. 2017 ELN Risk Stratification by Genetics

Risk category*	Genetic abnormality
Favorable	t(8;21)(q22;q22.1); RUNX1-RUNX1T1
	inv(16)(p13.1q22) or t(16;16)(p13.1;q22); CBFB-MYH11
	Mutated NPM1 without FLT3-ITD or with FLT3-ITD ^{low†}
	Biallelic mutated CEBPA
Intermediate	Mutated NPM1 and FLT3-ITD ^{high†}
	Wild-type NPM1 without FLT3-ITD or with FLT3-ITD ^{low†} (without adverse-risk genetic lesions)
	t(9;11)(p21.3;q23.3); MLL3-KMT2A ‡
	Cytogenetic abnormalities not classified as favorable or adverse
Adverse	t(6;9)(p23;q34.1); DEK-NUP214
	t(v;11q23.3); KMT2A rearranged
	t(9;22)(q34.1;q11.2); BCR-ABL1
	inv(3)(q21.3q26.2) or t(3;3)(q21.3;q26.2); GATA2,MECOM(EVI1)
	-E or del(5q); -or -or del(5q);
	Complex karyotype,§ monosomal karyotype
	Wild-type NPM1 and FLT3-ITD ^{high†}
	Mutated RUNX1 ¶
	Mutated ASXL1 ¶
	Mutated TP53 #

Frequencies, response rates, and outcome measures should be reported by risk category, and, if sufficient numbers are available, by specific genetic lesions indicated.

* Prognostic impact of a marker is treatment-dependent and may change with new therapies.

† Low, low allelic ratio (< 0.5); high, high allelic ratio (≥ 0.5); semiquantitative assessment of *FLT3-ITD* allelic ratio (using DNA fragment analysis) is determined as ratio of the area under the curve “*FLT3-ITD*” divided by area under the curve “*FLT3-wild type*”; recent studies indicate that AML with *NPM1* mutation and *FLT3-ITD* low allelic ratio may also have a more favorable prognosis and patients should not routinely be assigned to allogeneic HCT.^{57-59,77}

‡ The presence of t(9;11)(p21.3;q23.3) takes precedence over rare, concurrent adverse-risk gene mutations.

§ Three or more unrelated chromosome abnormalities in the absence of 1 of the WHO-designated recurring translocations or inversions, that is, t(8;21), inv(16) or t(16;16), t(9;11), t(v;11)(v;q23.3), t(6;9), inv(3) or t(3;3); AML with *BCR-ABL1*.

|| Defined by the presence of 1 single monosomy (excluding loss of X or Y) in association with at least 1 additional monosomy or structural chromosome abnormality (excluding core-binding factor AML).¹¹⁶

¶ These markers should not be used as an adverse prognostic marker if they co-occur with favorable-risk AML subtypes.

TP53 mutations are significantly associated with AML with complex and monosomal karyotype.

Appendix H. Two-Parameter BLRM Design

A 2-parameter Bayesian logistic regression model (BLRM, Neuenschwander et al, 2008) is used to guide dose escalation. The MTD target Toxicity Probability Interval (TPI) for DLT is (0.20, 0.33) and TPIs of (0.33, 0.60) and (0.60, 1.00) are defined as excessive and unacceptable, respectively. The design seeks to identify a dose most likely to have a DLT rate in the target TPI, but with overdose control that limits the possibility the dose has an excessive or unacceptable DLT rate (Babb et al, 1998). The probability of a DLT at dose level d_i is assumed to follow a Bernoulli distribution with probability p_i where the logit of p_i increases linearly with the log of the standardized dose in the following 2-parameter logistic model:

$$\log [p_i/(1-p_i)] = \text{logit}(p_i) = \log[a] + \exp(\log[b]) \log (d_i/d_{\text{ref}})$$

where a and b are random variables and d_{ref} is 1 of the planned dose selected as the reference dose.

A bi-variate normal prior distribution (Neuenschwander et al, 2008) was selected for $\theta = (\log a, \log b)$ where the probability that the true DLT rate is ≤ 0.40 at $\blacksquare \mu\text{g}$ is 0.90 and the probability the true DLT rate is ≤ 0.05 at the reference dose ($\blacksquare \mu\text{g}$) is 0.05. Additionally, the prior is such that p_i is approximately 0.05 for the $\blacksquare \mu\text{g}$ dose and 0.25 for the reference dose. Once the $\blacksquare \mu\text{g}$ is deemed safe by Dose Level Review Team (DLRT), the reference dose will be updated to the highest planned dose level.

The operating characteristics of the 2-parameter BLRM design were evaluated via simulation. The cohort size was fixed to 2 or 4 subjects. All simulated studies start with the multiple subject cohorts. The initial multiple subject dose level is $\blacksquare \mu\text{g}$ and subsequent doses were selected based on the following rules:

- After each cohort, the next dose is the one with the highest probability of the target TPI, but with a less than 0.25 probability of an excessive or unacceptable TPI.
- Skipping dose levels is not allowed.

Dose escalation was stopped given 1 or more of the following conditions:

- There have been at least 6 subjects treated at the dose recommended by the model.
- A maximum number of 36 subjects in the multiple subject cohorts is evaluated (note: this assumes that $n = 4$ subjects treated in single subject cohorts).

Operating characteristics are described below.

Operating characteristics

A total of [REDACTED] dose levels (unit: μg) were considered: [REDACTED] and [REDACTED] in these simulations of the multiple subject cohorts.

The design was evaluated for 3 possible dose-response scenarios: “Low,” “Mid,” and “High” MTD. [Table 30](#) shows the dose level and true probability of DLT for each scenario used in the simulated studies estimating the MTD. [Table 31](#) reports the operating characteristics from 10 000 simulated studies estimating the MTD when the target TPI is (0.20, 0.33). The rate of MTD selected and the number of subjects assigned to each dose level are presented in [Table 32](#).

[figure not shown]
[figure not shown]

Table 31. Operating Characteristics by Scenario for Simulated Studies Estimating the MTD When the Target TPI is (0.20, 0.33)

[figure not shown]
MTD Scenario	High		Mid		Low	
	4 subjects per cohort	2 subjects per cohort	4 subjects per cohort	2 subjects per cohort	4 subjects per cohort	2 subjects per cohort
Number of Subjects	24	14	20	14	16	10
Median (IQR)	(20 to 32)	(12 to 16)	(16 to 28)	(8 to 16)	(8 to 20)	(6 to 16)
Number of DLTs	3	2	4	2	6	4
Median (IQR)	(2 to 5)	(1 to 3)	(3 to 5)	(1 to 3)	(5 to 7)	(3 to 5)
Proportion of DLT (%)	14	14	20	21	40	42
Median (IQR)	(10 to 19)	(7 to 21)	(16 to 25)	(17 to 40)	(31 to 50)	(30 to 50)
Percentage of studies recommending dose with DLT probability of:						
≤ 10%	3.3%	24.7%	2.8%	13.8%	0.9%	9.0%
> 10% and ≤ 20%	31.8%	42.0%	26.7%	37.5%	25.0%	35.7%
> 20% and ≤ 33%	64.9%	33.3%	70.5%	48.7%	74.1%	55.3%
> 33%	0%	0%	0%	0%	0%	0%
Probability of identifying MTD to have 15% to 33% DLT probability	86.7%	60.6%	88.8%	76.1%	94.6%	82.7%

[figure not shown]
DLT = dose-limiting toxicity; IQR = interquartile range; MTD = maximum tolerated dose; TPI = toxicity probability interval.

[figure not shown]

Extremely Toxic Case

In addition, the performance of BLRM under the extremely toxic scenario was evaluated through simulations, where the DLT rate is expected to be high (the DLT rate exceeds 0.33 at all the tested dose levels) as shown in [Table 33](#). In this extremely toxic scenario, it is highly likely to have a Grade ≥ 2 treatment-related adverse event or DLT observed at the initial dose levels. Therefore, simulation results are presented in [Table 34](#) and [Table 35](#) by the dose level for initiation of the multiple subject cohorts.

Operating Characteristics for Standard 3+3 Design

As a comparison, the operating characteristics from 10 000 simulated studies estimating the MTD when using a standard 3+3 design are reported in [Table 36](#).

Table 36. Operating Characteristics by Scenario for Simulated Studies Estimating the MTD Using a 3+3 Design

MTD Scenario	High	Mid	Low	Extreme
Number of Subjects	14	15	14	12
Median (IQR)	(7 to 19)	(12 to 20)	(10 to 19)	(6 to 17)
Number of DLTs	3	3	4	4
Median (IQR)	(0 to 4)	(2 to 5)	(3 to 6)	(3 to 6)
Proportion of DLT (%)	17	23	30	36
Median (IQR)	(0 to 21)	(18 to 29)	(23 to 35)	(30 to 50)
Percentage of studies recommending dose with DLT probability of:				
≤ 10%	37.4%	39.8%	37.0%	23.7%
> 10% and ≤ 20%	62.6%	60.2%	63.0%	76.3%
> 20% and ≤ 33%	0%	0%	0%	0%
> 33%	0%	0%	0%	0%
Probability of identifying MTD to have 15% to 33% DLT probability	28.7%	18.4%	12.3%	14.3%

DLT = dose-limiting toxicity; IQR = interquartile range; MTD = maximum tolerated dose

Summary

The simulation results are summarized in [Table 31](#) and [Table 36](#). By comparing results in [Table 31](#) and [Table 36](#), we can see that while having a similar performance in controlling the number of DLTs in the trial, the 2-parameter BLRM design with the target TPI of (0.20, 0.33) has a similar or better performance in selecting the MTD, compared with the 3+3 design in the 3 scenarios.

